Exclusion criteria: Patients with previous prescription of opioid medication or non-opioid medication between 01.01.2012 and index treatment will be excluded. Patients with cancer treatment, palliative care or opioid substitution after index treatment will be excluded.

Follow-up: Patients' follow-up period include 5 years after start of opioid resp. non-opioid treatment and chronic pain diagnosis between 01.01.2013 and 31.12.2017. Each patient will be censored at death (death date), switching of study group (opioid --> non-opioid or vice versa), 12 months without treatment or followed-up 5 years until last known record for the patient in the German health claims database, latest at 31.12. 2017 (end of latest data cut), whichever happens first.

Variables:

Outcome Variables include death by any course as primary endpoint and hospitalization due to any course, hospitalization with misuse, addiction diagnoses, outpatient diagnosis of misuse or addiction and treatment procedures as secondary endpoints.

Exposure Variables are pain treatments including opioid and non-opioid treatments.

Other Covariates will be collected for assessments over the course of the study: Age and gender (sex: male, female), charlson comorbidity index. Comorbidities, comedications, region will be collected for Propensity Score Matching.

Data Analysis: The main analysis will focus on each of the 2 main cohorts with chronic pain patients as defined at inclusion and:

- with opioid treatment between 01.01.2013 and 31.12.2017 (named cohort A)
- with non-opioid treatment between 01.01.2013 and 31.12.2017 (named cohort B)

To address the group comparisons adequately, a propensity score matching will be conducted. The main analyses will include a multivariate Cox proportional hazards regression. Additional stratified analyzes will be carried out as follows: Subgroup analyses for each following pain conditions will be conducted: headache (R 51*); pain, not elsewhere classified (R52*); persistent somatoform pain disorder (F45.4*); polyneuropathy in diabetes (E10.4*-E14.4 plus G63.3), kyphosis and lordosis (M40), scoliosis (M41), spinal osteochondrosis (M42), other deforming dorsopathies (M43), ankylosing spondylitis (M45), other inflammatory spondylopathies (M46), spondylosis (M47), other spondylopathies (M48), and spondylopathies in diseases classified

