9.1 Study Design

This is a retrospective observational cohort study based on an anonymized German health claims database. This database contains data on around 4 million insured people from 69 German statutory health insurances (SHI). This research database is a complete, longitudinal claims dataset of approx. 7 million individual patients (ca. 10% of the statutory insured population of Germany) between 2012 and 2017. The analyses for this study will be done on a 4 million patients subset that is stratified by age

and gender based on the 2013 population structure of Germany as reported by the German Federal Statistical Office DeStatis.

This study consists of two cohorts: opioid and non-opioid patients. Only patients who started their therapy between 2013 and 2017 and had no therapy in 2012 (therapy naïve patients) will be included in the study.

Exposure time is defined as max. 5 years after the initial prescription for each patient, so that exposure time is max. 60 months per patient.

Exposure time may end before the end of study if patient died, stopped treatment (end of follow-up after 1 year without treatment with opioids / other pain medication), changed treatment group (from opioids to other pain medication or vice versa) or was lost to follow up due to other reasons (e.g. change of insurance), whichever occurs first.

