9.2.1 Study Period

Due to data protection regulations in Germany, only an extract of maximum 6 years of data coverage could be available for the research purposes: 1st January 2012 to 31st December 2017.

The **baseline period** is defined as the period prior to the date of first diagnosis of diagnoses or first opioid or non-opioid treatment initiation as described in inclusion criteria (Chapter 9.2.2.1). The baseline assessment period endures between January 01, 2012 and first study medication prescription.

Index treatment is defined as the date of first opioid or non-opioid treatment prescription between 1st January 2013 and 31st December 2017.

Exposure time is defined as time between index treatment and December 31, 2017. Considering data availability of a maximum of 6 years and prescription in a required time period of 60 months, exposure time endures maximum five years. Thus, patients can be censored at death (death date in the linked records), last known record for the patient in the German health claims database, switching of treatment groups (from opioid group to non-opioid group or vice versa), 12 months without opioid/non-opioid treatment or 31st December 2017 (end of latest data cut), whichever comes first.

[figure not shown]
The **outcomes** will be assessed between index treatment and 31.12.2017.

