9.2.2.2 Exclusion Criteria

Following exclusion criteria will be used to extract the eligible study population (see also Figure 2):

Cohort A and B:

- Patients with present opioid and non-opioid pain medication prescriptions in 2012 are excluded from analysis (therapy-naïve patients only).
- Cancer patients will be excluded if the cancer diagnosis is accompanied by at least one of the following treatments in the same quarter: radiation therapy or chemotherapy all defined by the codes in Table 9-3. Diagnoses will be assessed via ICD-10 diagnoses during the inclusion period from 1 January 2012 until index treatment and main and secondary hospital diagnoses (i.e. *Haupt- und Nebendiagnosen*) will be taken into account.
- Palliative care, coded by ICD-10 code Z51.5 or OPS code 8-982*, 8-98e*, 8-98h* before index date is excluded
- Opioid substitution treatment with ICD-10 code Z51.83 in the study period is excluded.

Table 9-3: Exclusion criteria for cancer patients

Name	ICD-10 Code	
Malignant neoplasms	C00-C97	
Plus at least one the following in the same quarter		
Name	Code	Type of Code
Palliative care	Z51.5	ICD-10
Chemo therapy	Z51.1	ICD-10
Radiation therapy	Z51.0	ICD-10
Chemo therapy	8-541* 8-542* 8-543* 8-544* 8-546*	OPS Code

Radiation therapy	8-52*	OPS Code
Palliative care	8-982* 8-98e* 8-98h*	OPS Code

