9.8.2 Sensitivity analysis

The following main sensitivity analysis will be conducted:

Sensitivity analysis
No cancer patients: Exclude all patients with at least one C00 – C96 diagnosis before index date

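### The synopsis and section 9.2.2.2 contradict each other on cancer and palliative care after index; neither rule is sound for the all-cause mortality HR, and no sensitivity analysis covers the gap

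*Protocol*

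**What the plan says.** Four parts of the protocol bear on this point.

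- **Exclusion, section 9.2.2.2.** A cancer code with a listed treatment in the same quarter excludes a patient, within a window that closes at index: "Diagnoses will be assessed via ICD-10 diagnoses during the inclusion period from 1 January 2012 until index treatment". Palliative care has the same limit: "Palliative care, coded by ICD-10 code Z51.5 or OPS code 8-982*, 8-98e*, 8-98h* before index date is excluded".
- **Exclusion, synopsis.** The window lies on the other side of index: "Patients with cancer treatment, palliative care or opioid substitution after index treatment will be excluded".
- **End of follow-up.** The synopsis has "Each patient will be censored at death (death date), switching of study group (opioid --> non-opioid or vice versa), 12 months without treatment", then last record or the end of 2017. Section 9.1 has "Exposure time may end before the end of study if patient died, stopped treatment", group change or loss to follow-up. Section 9.2.1 names death, last record, "switching of treatment groups (from opioid group to non-opioid group or vice versa), 12 months without opioid/non-opioid treatment or 31st December 2017". None of these lists, nor the one for the mortality rate in 9.4.2.1, names cancer or palliative care.
- **Sensitivity analysis, section 9.8.2.** The single entry is "No cancer patients: Exclude all patients with at least one C00 – C96 diagnosis before index date".

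The primary endpoint (9.4.2.1) is death from any cause. Under 9.3.2, CCI is taken at baseline, and only treatment dosage varies with time. The propensity score (9.3.1) models the choice of treatment.

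**The concern.** Pain can be the first sign of a cancer that has not yet been found. If such pain leads to an opioid more often than to a Cohort B drug, the later cancer death is credited to opioid treatment of noncancer pain. That is reverse causation. Baseline CCI and the propensity score cannot remove it, because the diagnosis does not yet exist when they are measured.

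The censoring rules open a second route that needs no imbalance at index. A Cohort B patient who develops cancer and is moved to an opioid is censored at the switch, so the death is lost to Cohort B. A Cohort A patient with the same cancer who stays on the opioid is followed to death.

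The synopsis rule does not solve this. It decides who belongs in the study by events after time zero that lie on the path to the outcome, and it deletes those patients' person-time and deaths altogether. At stake is whether a raised mortality HR can be read as a finding about noncancer pain.

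**Working it through.** The protocol states no effect size, event count or bias estimate, so there is no figure to reproduce. The check has two parts.

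**1. The two rules side by side**

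| Patient with first cancer or palliative code after index | Section 9.2.2.2 | Synopsis |
|---|---|---|
| Cancer treatment or palliative care after index | Stays in; no censoring at the code | Whole patient removed |
| Cancer code only, no treatment or palliative care | Stays in | Stays in |
| Covered by 9.8.2 | No | No |

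The first row gives opposite answers for the same patient. The second row is open under both rules.

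**2. Illustrative size under 9.2.2.2**

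Input from the protocol: expected mortality around 100 and 200 per 10,000 person-years (9.3.1). Assumptions not in the documents: true HR 1, mean follow-up 2 years, and an excess fraction *f* of Cohort A (over Cohort B) with a fatal cancer undiagnosed at index.

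Excess rate = *f* / mean follow-up × 10,000. Apparent HR = (base rate + excess) / base rate.

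| *f* | Excess per 10,000 PY | HR at 100 | HR at 200 |
|---|---|---|---|
| 0.5% | 0.005/2 × 10,000 = 25 | 125/100 = 1.25 | 225/200 = 1.13 |
| 1% | 50 | 1.50 | 1.25 |
| 2% | 100 | 2.00 | 1.50 |

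The excess falls in proportion as mean follow-up lengthens. At 2.75 years it is 18.2, 36.4 and 72.7, giving 1.18, 1.36 and 1.73 at 100, and 1.09, 1.18 and 1.36 at 200.

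A second model assumes instead that a share *d* of opioid person-time carries a death rate of 3,000 per 10,000 PY: ratio = [(1 − *d*) × base + *d* × 3,000] / base. For *d* from 0.5% to 2% this gives 114.5/100 = 1.15 to 158/100 = 1.58 at 100, and 214/200 = 1.07 to 256/200 = 1.28 at 200.

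**Switching route alone.** Assume equal cancer risk: 1% fatal cancer in each cohort over 2 years (50 per 10,000 PY), with half of the Cohort B cases censored at a switch before death (25 still counted). The ratio is (base + 50)/(base + 25): 150/125 = 1.20 at 100 and 250/225 = 1.11 at 200. This applies where switching censors (synopsis, 9.1, 9.2.1). The list for the mortality rate in 9.4.2.1 does not name switching.

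**The case against.** A reader might infer that the plan definitely counts deaths from undiagnosed cancer as deaths on opioids, and that such patients stay in Cohort A until they die. The document does not support either statement. Nothing gives 9.2.2.2 precedence over the synopsis, and under the synopsis most of these patients leave the analysis. Under 9.2.2.2, follow-up can still end earlier through a switch, 12 months without treatment, the last record or the data cut.

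The entry rules also weaken the mechanism. Cohort A needs consecutive opioid prescriptions over at least three quarters (9.2.2.1), which 9.4.1 reads as at least nine months, so many rapidly fatal cancers never enter. The synopsis also asks for pain diagnoses in at least three quarters before the first opioid claim; 9.2.2.1 is looser and requires only one before index. Cohort B drugs can be started for the same pain, so at index only the excess matters. These points reduce the bias. They do not remove cancers that become fatal later, or the asymmetry at switching.

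It can also be said that further sensitivity analyses belong in an SAP, and that 9.10.1.4 already admits unmeasured confounding. But the exclusion windows and censoring events are fixed in this protocol and conflict here. Section 9.8.2 addresses cancer only on the side of index that baseline data can already see. The admission on confounding does not mention reverse causation.

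Finally, the HR figures depend entirely on the assumed excess fraction. That stands, and they should be read only as showing what a small excess could do.

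**Conclusion.** The contradiction between the synopsis and 9.2.2.2 is certain from the text. So is the absence of any censoring rule or sensitivity analysis for cancer or palliative care first recorded after index. That this biases the mortality HR is plausible but not demonstrated. It requires either an excess of undiagnosed cancer in Cohort A at index, or Cohort B cancer patients being censored on a move to opioids. Because expected mortality is low, a small excess is enough: 0.5% to 2% of Cohort A would turn a true HR of 1 into 1.25 to 2.00 at 100 per 10,000 PY, or 1.13 to 1.50 at 200, with 2 years' mean follow-up and before allowing for the three-quarter minimum. The documents do not support treating any of these values as the expected bias. The point should be corrected before analysis; it does not invalidate the design.

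**What to change.** 1. Reconcile the synopsis with 9.2.2.2 so that cancer and palliative eligibility uses only information up to index.
2. Add to 9.8.2 two supportive analyses of the primary HR:
   - **Lagged.** Time zero is 12 months after index in both cohorts, excluding anyone with a C00-C97 or palliative code before that time zero. If the nine-month reading in 9.4.1 holds, the lag itself removes only about three further months in which deaths could occur, and most of the gain comes from the code exclusion.
   - **Censoring.** Both cohorts are censored at the first C00-C97 or palliative code after index. State that this censoring is informative, because such codes often come shortly before death, and that palliative codes are not specific to cancer.
3. Report both beside the primary HR, and qualify the noncancer conclusion if the estimate moves materially towards 1. Attach no pass-or-fail significance rule: a less precise lagged estimate could fail one for lack of events alone.

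Cost: an edit to the synopsis and two extra model runs on data already extracted. The lagged run will have fewer deaths and wider intervals.

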9.4.2.2 Secondary endpoints

Secondary endpoints are following:

- **Hospitalization due to any course.** Hospitalization will be assessed via the number of hospitalisations (calculated by counting the number of discharge dates (KH_Fall. Entlassungsdatum) in the year of interest, hospitalization rate, and length of stay in the hospital (KH_Fall. Verweildauer). The rate of hospitalization will be estimated as the number of patients with at least one hospitalization during the follow-up period divided by person-time of follow-up, censoring at time of death, last known record for the patient in the database, or 31st December 2017 (end of latest data cut), whichever is earlier.
- **Intensive care unit (ICU-stay)** stay is defined as patient's stay based on specialty of department in hospital (KH_OPS.Fachabteilung = 3600).
- **Hospitalization with to misuse or addiction.** The hospitalization with misuse or addiction will be analysed, if principal (main) diagnosis at discharge date between January 1st 2013 and December 31st 2017 contains at least one ICD-10 diagnosis of misuse/addiction: F10* or F11* or F13* or F19* or T40* (see also Appendix B in **Fehler! Verweisquelle konnte nicht gefunden werden.**).
- **Hospital admission diagnoses.** We report the hospital admission diagnoses based on ICD-10 codes between January 1st 2013 and December 31st 2017.
- **Coding of procedures in hospitals** that indicate number of patients that were hospitalized with severe diseases such as cardiovascular

diseases will be assessed via OPS-Codes provided in Appendix B as an excelsheet.

- **Coding of a misuse or addiction diagnosis in the outpatient sector** will be assessed via number of codings of misuse/addiction (ICD Codes = F10* or F11* or F13* or F19* or T40*) in outpatient sector by general practitioner or a specialist (e.g. psychiatrist), as ensured diagnosis (Diagnosesicherheit='G'). Additionally, the number of patients with a least one coding of ICD 10 codes of an ensured misuse/addiction in outpatient sector by general practitioner or a specialist (e.g. psychiatrist) will be assessed.
- **Sick leave** will be assessed as an absolute number and relative frequencies of patients with an attest of inability to work (patients with attest of inability to work as a percentage of all patients) in 2013-2017 and number of days being off work.
- **Hospital deaths** will be assessed via reason of discharge = death (Entlassgrund = Tod)

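### Opioid substitution coded after index removes patients from the cohort, and the synopsis contradicts section 9.2.2.2 on when the cancer and palliative-care exclusions apply

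*Protocol*

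**What the plan says.** Section 9.2.2.2 sets three exclusions for both cohorts, with different time windows.

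- **Opioid substitution:** "Opioid substitution treatment with ICD-10 code Z51.83 in the study period is excluded". There is no limit to the time before index. Section 9.2.1, headed Study Period, says that "only an extract of maximum 6 years of data coverage could be available for the research purposes: 1st January 2012 to 31st December 2017".
- **Palliative care:** "Palliative care, coded by ICD-10 code Z51.5 or OPS code 8-982*, 8-98e*, 8-98h* before index date is excluded".
- **Cancer with treatment:** diagnoses are assessed "during the inclusion period from 1 January 2012 until index treatment".

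The synopsis gives all three a single, different window: "Patients with cancer treatment, palliative care or opioid substitution after index treatment will be excluded".

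Section 9.2.1 says that outcomes "will be assessed between index treatment and 31.12.2017". Section 9.4.2.2 measures addiction in outpatient care as the "number of codings of misuse/addiction (ICD Codes = F10* or F11* or F13* or F19* or T40*) in outpatient sector", and uses the same code list for the principal diagnosis of a hospital stay.

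**The concern.** Eligibility should be settled by what is known at index. Under both the synopsis and section 9.2.2.2, a patient who starts follow-up normally and is later coded Z51.83 is removed from the study altogether, together with that patient's person-time, hospital stays, addiction codings and any death.

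Z51.83 is not itself an outcome code. But a patient in opioid substitution plausibly also carries F11*, which is one. The rule can therefore delete cases of the outcome named in the secondary objective of section 8.2. If this happens more often in cohort A than in cohort B, the addiction ratio is pushed down: toward no difference when the true ratio exceeds 1, and below 1 when the true risks are equal.

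The second problem is a plain contradiction. For cancer treatment and palliative care, the synopsis and section 9.2.2.2 name opposite sides of the index date. If the synopsis were followed, patients close to death would be removed from a study whose primary endpoint is death from any cause.

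**Working it through.** **Step 1: the windows side by side**

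| Exclusion | Synopsis | Section 9.2.2.2 |
|---|---|---|
| Cancer plus treatment | after index | 1 January 2012 until index |
| Palliative care | after index | before index |
| Opioid substitution (Z51.83) | after index | study period |

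The meaning of study period matters only for the last row. The heading and dates of section 9.2.1 give 2012 to 2017. Section 9.2.2.1, in the sentence that introduces Table 9-2, names the time from 1 January 2012 to index and the study period as two separate windows, so the phrase is not shorthand for baseline. Even a 2013 to 2017 reading would include time after index. Both texts therefore reach past index for Z51.83. They oppose each other only on cancer and palliative care. There, the sensitivity analysis in section 9.8.2 sides with 9.2.2.2: "Exclude all patients with at least one C00 – C96 diagnosis before index date". The synopsis is the outlier.

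**Step 2: addiction outcome (illustration)**

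The protocol states no figure that depends on these windows, so there is nothing to reproduce. It also gives neither the frequency of Z51.83 nor its overlap with the outcome codes. Every input in this step is an assumption.

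Let p be the true risk in a cohort and q the share of its cases deleted for a later Z51.83 code. Deletion removes cases from numerator and denominator, so the observed risk is p(1 − q)/(1 − pq). Take pA = 0.010 and pB = 0.005, a true ratio of 2.0.

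Example with qA = 0.05 and qB = 0: (0.010 × 0.95)/(1 − 0.0005) = 0.009505, and 0.009505/0.005 = 1.90.

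| qA | qB | Observed ratio |
|---|---|---|
| 1% | 0 | 1.98 |
| 5% | 0 | 1.90 |
| 10% | 0 | 1.80 |
| 25% | 0 | 1.50 |
| 40% | 0 | 1.20 |
| 5% | 5% | 2.00 |
| 5% | 10% | 2.11 |

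The result hardly depends on the assumed base risks. With 2% against 1%, removing 5%, 10% or 40% of cohort A cases gives 1.90, 1.80 or 1.21. With equal risks of 2% (true ratio 1.00), removing 5% or 10% in cohort A only gives 0.95 or 0.90.

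**Step 3: mortality, only if the synopsis wording were applied (illustration)**

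Section 9.3.1 expects mortality of around 100 and 200 per 10,000 person-years but does not assign these figures to cohorts. Giving 200 to cohort A is an assumption, and so are the shares of deaths removed, rA and rB. Ignoring the small loss of person-time, the ratio is 200(1 − rA)/[100(1 − rB)].

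- 40% in A, 10% in B: 120/90 = 1.33
- 20% in both: 160/80 = 2.00
- 10% in A, 40% in B: 180/60 = 3.00

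The ratio can move either way, and stays put if the shares are equal.

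**The case against.** - **The substitution rule may be deliberate.** Both texts reach past index here, and the study opioids in Table 9-1 include buprenorphine, so the authors may have wanted substitution patients kept out of a pain cohort. The protocol states no such reason, and a window before index screens out known substitution without using the future. Other events after index, such as switching group or 12 months without treatment, lead to censoring in section 9.2.1, not deletion.
- **The larger addiction scenarios are not supported.** The outcome also covers F10*, F13*, F19* and T40*, so removing 25% to 40% of all cohort A cases would need a substitution code in a large part of the whole composite. This stands: those rows show only how the ratio responds. The plan also counts codings and uses chi-squared and t-tests, so a risk ratio is a simplification.
- **The synopsis conflict is a drafting error.** Section 9.2.2.2 is the detailed text and already uses a window before index for cancer and palliative care. This limits the weight of the point and makes the mortality figures secondary. It does not remove the need to reconcile, because section 9.6.1 says the data are obtained on the basis of this protocol.
- **A rule tied to the index date needs more detail.** Section 9.2 records outpatient diagnoses only by quarter, so a code in the index quarter cannot be placed before or after index. This stands and is taken up in the fix.

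**Conclusion.** The concern holds on both counts and should be fixed. The Z51.83 rule selects patients on an event after index, and the synopsis contradicts section 9.2.2.2 on the timing of the cancer and palliative exclusions. Both follow from the text with high confidence.

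The size is uncertain. The addiction comparison, a secondary objective, is biased downward only if deletion takes a larger share of cases in cohort A than in cohort B. For assumed removal of 1% to 10% of cohort A cases and none in B, a ratio of 2.0 falls to between 1.98 and 1.80. The protocol has no counts with which to narrow this. The primary endpoint is at risk from the cancer and palliative exclusions only if the synopsis wording is used, and then in either direction.

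**What to change.** 1. In section 9.2.2.2, limit the Z51.83 exclusion to codes from 1 January 2012 until the index date, in both cohorts.
2. In the synopsis, change the timing of all three exclusions from after index to before index, and check that Figure 2 agrees.
3. State how an outpatient code dated only to the index quarter is treated, for example by counting only quarters completed before the index date, with the same rule in both cohorts.
4. Keep patients with a first Z51.83 code after index, count their addiction events through the existing F10*, F11*, F13*, F19* and T40* definitions, and state that their follow-up continues under the existing censoring rules. A patient with Z51.83 but none of the qualifying codes would not count as a case.
5. Optionally, add a sensitivity analysis that censors at the first Z51.83 code.

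The cost is a few wording edits. No new data are needed and no endpoint changes.
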